7.1.3 Other study parameters

We assume that potential effects of ghrelin are mediated by mild neuronal activation, preventing ill-fated neuronal inactivity. This is based on studies under experimental in vitro and in vivo conditions.^{10,18} To study effects of ghrelin on neuronal activity, we consider brain activity as measured by the EEG. Continuous EEG measurements during day 0-3 after

cardiac arrest are performed in all participating hospitals in the context of current care. The following EEG measures will be extracted and studied in relation to ghrelin treatment: the temporal brain symmetry index (tBSI),²⁴ the cerebral recovery index (CRI)²⁵ and EEG background continuity.²⁶ All three measures strongly represent restoration of brain activity after an hypoxic insult and are strongly related to clinical recovery.

7.2 Randomisation, blinding and treatment allocation

Subjects after cardiac arrest and successful cardiopulmonary resuscitation that are admitted to an intensive care unit of a participating hospital can be considered for enrolment in the study. Randomisation will be 1:1, in blocks of N=10, stratified by study site. Randomisation will be performed if the subject meets all inclusion/exclusion criteria and will be processed centrally by means of a web-based system that will provide the randomisation treatment arm (Ghrelin or placebo). The online system (Research Manager®), is constructed and validated for randomization and data management and has an audit trail. Contact persons of all participating centres can sign in and randomize their patients.

A legal representative or family member will be informed and patients will be included on the intensive care by their treating intensive care physician. Once informed consent is obtained, the collaborating hospital pharmacist will be notified by the intensive care physician. The pharmacist will sign in Research Manager, include the patient and randomize. The pharmacist will receive the treatment allocation through Research Manager, and thus be unblinded. He / she will prepare the treatment or placebo and provide it to the treating intensive care physician. The intensive care physician will remain blinded to the treatment allocation.

The investigator can decide to withdraw a subject from the study for urgent medical reasons. In this case the investigator can decide to 'unblind' the patient. For unblinding, the unblinded collaborating pharmacist will provide information on the treatment allocation to the treating intensive care physician.

7.3 Study procedures

All comatose patients after cardiac arrest will be admitted to intensive care units to receive treatment according to guidelines, as described in national and local ICU protocols.

A legal representative or family member of all eligible patients will be informed about the study as soon as possible after admission on the ICU by the ICU staff/research coordinators. Since any beneficial effect of the treatment under study is assumed to be larger with earlier

initiation, randomization and treatment should be initiated within 12 hours after cardiac arrest (ROSC). All participating centers have ample experience with inclusion of patients with acute cardiac arrest or cerebral ischemia in intervention studies.

Patients who are enrolled in this trial will receive intravenous treatment with acylated ghrelin 600micrg twice daily vs. placebo. The duration of the treatment is one week. This treatment duration of one week will be adhered to, both in patients that remain comatose, and in patients that awaken within a week. If patients are transferred from the ICU to a cardiac care unit or general ward within one week, treatment will be continued for a total of one week, as well. Intravenous treatment will be administered through infusion systems that are already in situ in all of these patients. There will be no additional punctures.

Baseline data will be obtained at admission as part of regular patient care and include: clinical data, EEG data, medical history, and use of medication. In addition, a venous blood samples (5cc) will be taken to measure the baseline ghrelin concentration. This sample will be collected during routine blood sampling; there will be no additional punctures.

After randomization, daily physical, neurological, and additional examinations at the ICU will be part of routine patient care. In addition, there will be blood sampling for measurement of ghrelin concentrations at day 1 and 3, measures of neuronal damage (NSE at day 1-3), measures of cardiac damage (troponine and CK/CK-MB ratio at day 0-3), hormone concentrations (cortisol, growth hormone, prolactine, ACTH, IGF-1 at day 1-3), and highest glucose levels at day 1-7. All blood samples will be collected during routine blood sampling, if possible; preferably, there will be no additional punctures. However, blood sampling for measurement of ghrelin concentrations will be done at 30±15 minutes after treatment with ghrelin or placebo. For these measurements additional blood samples will be taken, if necessary.

Apart from the study treatment and the venous blood sampling, patients will not be subjected to additional procedures during admission.

Surviving patients will be asked informed consent for participation and additional follow-up on long term outcome. Follow up at 3 and 6 months in surviving patients will be done by telephone interview by a trained research nurse three and six months after admission. The nurse will collect CPC scores based on a standard interview. At twelve months, patients will be invited to the nearest hospital or visited at their place of residence for detailed neuropsychological examination (please see F1 testbatterij NPO for details of the test

battery). Separate informed consent will be asked for neuropsychological examination at twelve months.

Table. Overview of study procedures

	Baseline (Day 0)	Day 0-6	Day 1-7	Day 7	3m	6m	12m
Ghrelin/ placebo treatment		X					
Venous blood sampling (largely within current care)	X		X				
CPC scores				X	X	X	
Neuropsychological examination							X

M = months, CPC = Cerebral Performance Category, to be collected by a telephone interview

The total burden in hours for the patient is max 12 hours. This includes multiple transfusions of the study drug, venous blood sampling, and the follow-up procedures at 3, 6 and 12 months.

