4.4 Sample size calculation

This is a phase 2 trial aiming at estimation of safety and potential of efficacy. Power calculations are hampered by lack of any data on ghrelin effects in patients with postanoxic encephalopathy. An intended sample size of 160 patients is based on analysis of any shift in the direction of a better outcome on the CPC scale, a mean CPC score without treatment at six months of 3.20, SD of 1.8 (based on our observations on natural history in 277 patients)⁷, a mean difference between treated and untreated patients of 0.8 points on the CPC scale, alpha of 0.05 and power of 80%. The mean difference of 0.8 points on the CPC scale may be an overestimation of potential benefit. The consequent relatively small sample size is considered justified, given the need for larger future phase 3 trials if potential benefit is demonstrated. Interim analyses will only be directed at safety (comparison of SAEs between treatment groups), so no additional subjects need to be included to compensate for interim analyses.

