7.1.2 Secondary study parameters/endpoints

Secondary outcomes include case fatality at one week and 6 months, time to awaken (time interval between resuscitation and GCS score of 14), EMV score and estimated CPC score at 1 week, CPC score at 3 and 12 months, and cognitive functioning at 12 months.

Cardiovascular secondary outcome measures are:

Mean arterial blood pressure day 1-7 (mean, highest, lowest)

Heart rate day 1-7 (mean, highest, lowest)

Arrhythmia day 1-7: yes / no. If yes: type of arrhythmia

Cumulative dose of vasopressive medication day 1-7

Cumulative dose of inotropic medication day 1-7

Sequential Organ Failure Assessment score day 1-7

Kidney function day expressed as GFR day 1-7

CVVH day 1-7: yes / no

Assist devices day 1-7: yes / no

Biomarkers are:

Cardiac: troponine and CK / CK-MB ratio at day 0, 1, 2 or 3

Neurological: NSE day 1, 2, 3

Endocrinological: cortisol, growth hormone, prolactine, ACTH, IGF-1 day 1, 2, 3

Highest glucose levels at day 1-7

Gastro-intestinal outcome measure is: gastric residual volume (day 1-7, during ICU admission)

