9.2 Secondary study parameter(s)

With regard to the range of secondary outcome parameters, we will use simple 2x2 tables, two-group t-tests, Mann-Whitney tests, or multivariable linear and logistic regression models, where appropriate. In all analyses, statistical uncertainty will be quantified by means of 95% confidence intervals. Subgroup analyses based on the EEG pattern at 24 hours will be carried out for the following subgroups: (1) suppressed patterns and suppressed patterns with synchronized periodic activity, (2) continuous patterns, and (3) other patterns. This is based on our previous studies on EEG based outcome prediction of comatose patients after cardiac arrest, where the first subgroup represents patterns that are strongly associated with a poor prognosis, the second subgroup with a good prognosis, and the third subgroup with an intermediate prognosis.[refs] Although the size of this study will not allow for precise estimates of treatment effect in subgroups, we will assess heterogeneity of effects, and analyze consistency of effects on secondary outcomes.

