Our study population consists of freshly resuscitated patients after cardiac arrest. These patients suffer from a life threatening disease and may be hemodynamically unstable. All patients are admitted to an intensive care unit. Our study population may be exceptionally vulnerable to cardiovascular adverse events.

In previous studies, cardiovascular effects of ghrelin were beneficial rather than detrimental. In healthy men, low-dose ghrelin infusion was associated with increased mean peak myocardial systolic velocity.⁴⁰ A large ghrelin iv bolus increased stroke volume and decreased systemic vascular resistance and mean arterial pressure (MAP) in healthy volunteers,⁴¹ although a similar dose of sc ghrelin increased LVEF without change in MAP.⁴² In participants with heart failure, higher and repeat dose infusions decreased MAP, pulmonary capillary wedge pressure, and systemic vascular resistance and increased cardiac index, stroke volume, and LVEF; these changes were associated with improved exercise capacity.^{43,44} In these previous studies, cardiac effects of ghrelin were dose and route dependent, with greater potency from iv ghrelin compared to the sc route.

h. Interaction with other products

We know of no relevant pharmacokinetic or pharmacodynamics interactions between ghrelin and standard treatment modalities for patients after cardiac arrest.

i. Predictability of effect

There are no known biomarkers for effect of ghrelin on neurological or cardiovascular outcomes.

j. Can effects be managed?

There are no antidotes or antagonists available. Since all patients are initially admitted on intensive care units, access to adequate medical support is guaranteed.

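### One of the two cardiac damage markers is written as the CK/CK-MB ratio, a relative measure that does not track the amount of damage and, under the usual premise for CK-MB, runs opposite to troponin

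*Protocol*

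**What the plan says.** Section 7.3 describes the blood sampling after randomisation and includes "measures of cardiac damage (troponine and CK/CK-MB ratio at day 0-3". Section 7.1.2 lists the secondary outcome as "Cardiac: troponine and CK / CK-MB ratio at day 0, 1, 2 or 3", and section 2 uses the same words under the secondary objectives, which cover both safety and efficacy. In all three places troponin comes first, and total CK stands before CK-MB in the ratio.

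No section lists absolute CK-MB or absolute total CK as an outcome, says whether a high or a low ratio is favourable, or gives an expected value, spread or cut-off. For secondary outcomes section 9.2 says only that "we will use simple 2x2 tables, two-group t-tests, Mann-Whitney tests, or multivariable linear and logistic regression models, where appropriate".

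**The concern.** A marker of damage should grow with the amount of damage. A quotient of two enzyme values shows their relative size, so a common rise in both leaves it where it was. With total CK on top, more CK from the heart should also lower the value, while troponin rises. The list would then hold two markers of the same injury that move in opposite directions, without saying so.

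Section 12.1 states that "Our study population consists of freshly resuscitated patients after cardiac arrest" and that this population may be especially vulnerable to cardiovascular adverse events. A cardiac injury marker is therefore read for safety as well as for efficacy. One that is insensitive, or easily read the wrong way round, weakens both.

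**Working it through.** **Inputs from the protocol.** The ratio as worded in sections 2, 7.1.2 and 7.3, and the sample size. Section 4.4 gives no figure for the ratio. Its total of 160 serves here only to fix the arm size. It rests on "a mean difference between treated and untreated patients of 0.8 points on the CPC scale, alpha of 0.05 and power of 80"%, with "a mean CPC score without treatment at six months of 3.20, SD of 1.8". Check: n per arm = 2 × (1.96 + 0.84)² × 1.8² / 0.8² ≈ 79.5, so 80 per arm and 160 in total, with power 80.3%. Section 7.2 gives 1:1 allocation. The protocol's figure reproduces.

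**Assumptions, none of them in the protocol.** C is CK from the heart and S is CK from other tissue. f and g are the CK-MB shares of each, with f = 0.10-0.30 and g = 0.01-0.05. That resuscitated patients have some S is plausible, but the protocol does not state it.

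**Algebra.** R = (C + S) / (fC + gS).

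- If S = 0, R = 1/f whatever the size of C.
- If C and S are multiplied by the same factor, the factor cancels and R is unchanged.
- dR/dC = S(g − f) / (fC + gS)². With S > 0 and f > g this is negative, so R falls as cardiac release rises.
- If f = g, R is constant at 1/f and carries no cardiac information. The premise f > g is therefore the only reason to use CK-MB as a cardiac marker at all.

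**Ten-fold damage, f = 0.15, g = 0.01.** C = 500, S = 0: 500/75 = 6.7. C = 5000, S = 0: 5000/750 = 6.7.

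**Same heart, more other CK.** C = 1000, S = 500: 1500/155 = 9.7. C = 1000, S = 4000: 5000/190 = 26.3.

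**A 30% cut in cardiac release, C from 1000 to 700, same f and g.**

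| Other CK | Ratio before | Ratio after | CK-MB before | CK-MB after |
|---|---|---|---|---|
| S = 0 | 6.67 | 6.67 | 150 | 105 |
| S = 500, fixed | 9.68 | 10.91 | 155 | 110 |
| S = 2000, fixed | 17.65 | 21.60 | 170 | 125 |
| S from 500 to 350 | 9.68 | 9.68 | 155 | 108.5 |

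Over the whole grid of f and g, with S fixed at 100, 500 or 2000, the same cut raised the ratio every time. The rise ran from 0.11 (3.61 to 3.72 at f = 0.30, g = 0.05, S = 100) to 5.00 (25.00 to 30.00 at f = 0.10, g = 0.01, S = 2000).

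**Power by simulation.** 80 per arm, Mann-Whitney test, C and S log-normal with log-SD 1, f = 0.15, g = 0.01, median S at 0.1 to 2 times median C. "Varying" lets f differ between patients with log-SD 0.4.

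| Reduction in cardiac release | Cardiac CK-MB share | Ratio | Absolute CK-MB |
|---|---|---|---|
| 50% | fixed | about 85-88% | about 97-99% |
| 50% | varying | about 30-78% | about 97-98% |
| 20% | both | about 7-17% | about 22-28% |

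Repeat runs move these by a few points. The rank correlation of the ratio with cardiac release is about −0.7 with fixed fractions and −0.26 to −0.60 with varying ones. Each correlation belongs with the power figures of its own model.

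**The case against.** Several points on the other side stand.

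- A reader might infer that the whole cardiac damage assessment rests on the ratio. It does not. Troponin is named beside it in all three sections, is not a ratio, and could still show an effect.
- A reader might infer that the plan would report a benefit as harm. No section says that a higher ratio is worse, and someone who knows that total CK is on top would read a rise as a smaller cardiac share. The documents support a risk of misreading only.
- A reader might infer that the ratio always cancels the size of the injury. Exact cancellation needs no other CK, or other CK changing in proportion. With independent other CK and fixed fractions the ratio does detect a large effect, at about 85-88% power, with the sign reversed.
- The wording may be shorthand for CK and CK-MB, or for the inverse index. The text does not settle this. That argues for clarifying it. Inverting the ratio would mend only its direction: the scale would still cancel, and a rank test would give the same power.
- The CK-MB shares and the source of other CK come from outside the documents, and the 50% reduction has no basis in them. At 20% neither marker is well powered, though CK-MB remains the better.

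The objection that derivation belongs in a statistical analysis plan carries only in part. How to transform or adjust CK-MB can be left there. Which quantity is the outcome is already fixed, in three places, by the protocol.

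**Conclusion.** The concern holds for one of two cardiac markers in the secondary outcomes. As written, the ratio is unchanged by a common scaling of cardiac and other CK. Given f > g and some other CK, it moves opposite to cardiac damage and to troponin. The algebra needs no further assumption. The loss of power does: it ranges from about ten points (50% reduction, fixed fractions) to well over half of the power (varying fractions, little other CK), and depends on release fractions that the protocol does not give.

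The six-month CPC analysis, the troponin outcome and the stated stopping criteria (SAEs, SUSARs, other safety issues) are untouched. This is a defect in a secondary biomarker, worth correcting because the correction is cheap and cardiac injury bears on safety here.

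**What to change.** In sections 2, 7.1.2 and 7.3, name absolute CK-MB as the cardiac damage marker beside troponin, and report total CK separately. If a ratio is kept, define it as CK-MB/CK, say which direction means a larger cardiac share, and label it descriptive.

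The cost is a change of wording in three places. Both values must be measured to form the ratio, so no new sample or assay is needed. The small downside is that absolute CK-MB also contains some non-cardiac CK-MB and may differ between site assays. Randomisation is stratified by site, which helps to balance assay differences between the arms.

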5. TREATMENT OF SUBJECTS

The trial treatment will consist of intravenous treatment with acylated ghrelin 600micrg dissolved in 50cc normal saline by bolus (short term) infusion in at least 30 minutes twice daily, for 1 week vs. placebo (i.e. 50cc normal saline without ghrelin).¹⁷ Treatment duration of one week is chosen because (i) ill-fated neuronal inactivity is mainly observed in the acute phase (first days) after cardiac arrest and (ii) previous phase 0 and 1 studies have proven safety with a treatment duration of one week.¹⁷

This trial treatment will be additional to current care. This indicates that all patients are treated according to national and local protocols for comatose patients after cardiac arrest. This includes targeted temperature treatment at 36°C in all participating centers.

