6.5 Description and justification of route of administration and dosage

Justification of intravenous route: In all preclinical and clinical studies, intravenous administration was used, either as a bolus or as continuous infusion.¹⁷

Justification of bolus infusion (which in this study is not bolus infusion in a narrower sense, but rather short term infusion in at least 30 minutes): We chose for bolus (short term) infusion, because (1) bolus (short term) infusion suits with the natural evolution of endogenous ghrelin concentrations, which fluctuates over time, and (2) in human studies, effects of ghrelin were largest with bolus infusions as compared with continuous infusion.¹⁷ There was no difference in the percentage of participants experiencing relevant adverse events between bolus and infusion routes of administration.¹⁷ However, somnolence and fatigue occurred more often with bolus infusion. Therefore, to minimize the risk of relevant side effects, instead of bolus infusion in a narrower sense, we chose to apply short term infusion in with an infusion rate of max 10 µg/kg/30min, which indicates an infusion time of at least 30 minutes.

Justification of dosage: Starting point for the chosen regimen of 600µg/dose, two times daily, was optimization of the probability of treatment effect. The highest tested and safe dose regimen is 10µg/kg/dose for single doses. The highest tested regimen for treatment during one week or more is 3µg/kg/dose, two times daily, in human studies. In animal studies, intraperitoneal application of 10-200µg/kg/dose, two times daily during 3-8 weeks, was safe. Given these data, and with an elimination half-life of 27 to 31 minutes,²³ we chose for max 10µg/kg/dose, infused in at least 30 minutes. In close deliberation with the collaborating intensive care physicians, we chose a fixed quantity of 600µg/dose for pragmatic reasons. This is equal to approximately 7.5-10µg/kg/dose. Larger ghrelin doses possibly increased the risk of flushing, as indicated by the higher rate of flushing in the 2 ghrelin bolus studies that employed the largest tested dose (10µg/kg).¹⁷ However, there was no association between dosage and serious adverse events.

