At the doses evaluated in the 66 published studies with adverse event reporting, ghrelin demonstrated an excellent short-term safety profile with few adverse effects.¹⁷ Serious adverse events such as pneumonia, enteritis, and lung cancer were extremely rare and difficult to attribute biologically to ghrelin administration. Most of the severe adverse events derived from 1 study of ghrelin v.s placebo administration in severely ill patients with pulmonary cachexia, a group that is vulnerable to developing additional medical problems.¹⁹ Mild adverse events occurred in approximately 20% of participants receiving ghrelin. The most common effect was transient flushing, which occurred in 10% of volunteers, but resulted in discontinuation of study medication in only 3 of the 939 participants in whom

adverse event collection was reported.²⁰⁻²² There was no difference in the percentage of participants experiencing flushing between bolus and infusion routes of administration. Larger ghrelin doses may increase the risk of flushing, as indicated by the higher rate of flushing in the 2 ghrelin bolus studies that employed the largest tested dose (10µg/kg). The most common gastrointestinal side effect was gastric rumbles, which occurred in 22 participants (2.3%) and was never severe enough to lead to ghrelin discontinuation. Gastrointestinal side effects and increased thirst were more common in volunteers who received continuous ghrelin infusions, perhaps due to the longer duration of exposure to ghrelin. Few participants developed neurocognitive effects including somnolence, fatigue, vertigo, or change in mood (26 subjects, 2.8%). These effects were more common in subjects who received ghrelin bolus, potentially due to the rapid ghrelin delivery.¹⁷ To minimize risks, we chose to apply short term infusion in at least 30 minutes, rather than bolus infusion in a narrower sense.

f. Pharmacokinetic considerations

Intravenously administered ghrelin is rapidly cleared. Fifteen minutes after administration of a single 1 or 5µg/kg bolus, total ghrelin plasma concentrations rose to 1059 and 6599fmol/l, from a mean baseline level of 169. Elimination half-life was 27 to 31 minutes.³⁶ A 61-fold increase in circulating total ghrelin has been reported 1 minute after iv injection of 10µg/kg with an elimination half-life of 10 minutes.

g. Study population

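### Cortisol, growth hormone, prolactin and ACTH are sampled without reference to the infusion and without a stated pre-dose value, so short-lived effects may be missed or diluted

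*Protocol*

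**What the plan says.** Protocol section 7.1.2 lists the hormones among the secondary biomarkers by day only: "Endocrinological: cortisol, growth hormone, prolactine, ACTH, IGF-1 day 1, 2, 3". Section 7.3 repeats days 1 to 3 and gives a general rule for blood sampling: "All blood samples will be collected during routine blood sampling, if possible; preferably, there will be no additional punctures". It then makes one exception: "However, blood sampling for measurement of ghrelin concentrations will be done at 30±15 minutes after treatment with ghrelin or placebo". That exception covers ghrelin concentration on days 1 and 3, and extra samples are allowed for it if needed.

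For the baseline draw, section 7.3 says that "a venous blood samples (5cc) will be taken to measure the baseline ghrelin concentration"; no hormone is named. The schedule table puts treatment on days 0 to 6, so every listed hormone sample falls after treatment has started. Troponin and the CK/CK-MB ratio, by contrast, have a day 0 value.

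Treatment is given "by bolus (short term) infusion in at least 30 minutes twice daily, for 1 week vs. placebo" (section 5). Section 6.5 justifies the dose "with an elimination half-life of 27 to 31 minutes". Section 12.1, item f, repeats that range and also cites a 10-minute half-life. Sections 1, 6.3 and 12.1 state that there is strong evidence that ghrelin raises growth hormone, ACTH, cortisol, prolactin and glucose. IGF-1 is not in that list.

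**The concern.** The drug clears quickly and is given in short infusions twice a day. The protocol controls the sampling time for the drug level but not for the hormones that the drug is expected to move. If the hormone response is brief, samples taken at arbitrary times mix patients caught during the response with patients sampled hours later, and the difference between arms shrinks towards zero. With no pre-dose value, the analysis also cannot remove differences between patients that were present before treatment.

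What is at stake is the interpretation of a secondary endpoint. These hormone rises are among the best-supported human effects that the protocol cites, and section 6.3 says ghrelin has not been given to comatose patients after cardiac arrest before. An analysis plan cannot repair this later: a pre-dose value that was not collected is lost, and so is the time since infusion if it was not recorded.

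**Working it through.** The protocol gives no power or sample size for the hormones, so there is no stated figure to reproduce.

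**Inputs from the protocol**
- Half-life h: "Elimination half-life was 27 to 31 minutes" and, from another report, "A 61-fold increase in circulating total ghrelin has been reported 1 minute after iv injection of 10µg/kg with an elimination half-life of 10 minutes" (both section 12.1, item f). Values used: 10, 27 and 31 minutes.
- Infusion of at least 30 minutes, twice daily (section 5). Value used: 30 minutes.
- Timed ghrelin window: 15 to 45 minutes after treatment (section 7.3).

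**Assumptions not in the protocol**
- Doses 12 hours (720 minutes) apart.
- Draw times spread evenly over that interval.
- First-order decay after the infusion ends.

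**1. Share of the interval with ghrelin above 10% of its end-of-infusion increment**

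The time to reach 10% is h × log2(10) = 3.32h. The share is (30 + 3.32h)/720.
- h = 10: (30 + 33)/720 = 8.8%
- h = 27: (30 + 90)/720 = 16.6%
- h = 31: (30 + 103)/720 = 18.5%

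**2. The same with a 5 half-life cut-off (0.5^5 = 3.1% remaining)**

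| h (min) | 30 + 5h (min) | Share of interval | Draws after this point |
|---|---|---|---|
| 10 | 80 | 11.1% | 88.9% |
| 27 | 165 | 22.9% | 77.1% |
| 31 | 185 | 25.7% | 74.3% |

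With cut-offs from 3 to 7 half-lives, the share of draws after clearance runs from 65.7% (h = 31, 7 half-lives) to 91.7% (h = 10, 3 half-lives). Each extra 30 minutes of infusion would lower these shares by 30/720 = 4.2 percentage points.

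**3. Level remaining, 0.5^(t/h), at t minutes after the end of infusion**

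| t | h = 10 | h = 27 | h = 31 |
|---|---|---|---|
| 15 | 35% | 68% | 72% |
| 30 | 12.5% | 46% | 51% |
| 45 | 4% | 31.5% | 37% |
| 180 | <0.001% | 1.0% | 1.8% |
| 330 (mid-interval) | about 0 | 0.02% | 0.06% |

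The first three rows are the window already set for ghrelin, read as counting from the end of infusion. An untimed draw falls in that 30-minute window with probability 30/720 = 4.2%.

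**4. From drug to hormone**

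The steps above describe ghrelin, not the hormones, and the protocol gives no time course for any hormone response. As an illustration, suppose an on/off response of duration D and a constant standard deviation. The mean difference is then multiplied by f = D/720, and the sample size for equal power by 1/f².
- D = 2 h: f = 120/720 = 17%, multiplier 36
- D = 3 h: f = 180/720 = 25%, multiplier 16
- D = 6 h: f = 360/720 = 50%, multiplier 4

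Dilution is therefore material even if the response far outlasts the drug, and its size depends strongly on a duration that the documents do not supply.

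**The case against.** The strongest counter-argument is that the half-life belongs to ghrelin while the endpoint is hormone concentration. Repeated dosing could shift a slowly or cumulatively responding hormone at any sampling time. This stands. It is why the figures in steps 1 to 3 cannot be read as the share of uninformative hormone samples.

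A reader might infer that a null hormone result would mean nothing, or that a neutral trial could not tell an inactive drug from late sampling. The documents do not support either reading. The protocol nowhere names the hormones as its check on drug activity. Section 7.1.3 assigns the study of neuronal activity to continuous EEG on days 0 to 3. Exposure is checked by the timed ghrelin samples. Daily highest glucose on days 1 to 7, another variable that ghrelin is said to raise, does not depend on a single routine draw.

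A reader might also infer that the missing baseline biases the comparison. In a 1:1 randomised trial it does not. It costs precision and the description of change within patients.

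Two further points are fair. Routine draws and infusions may both follow ward schedules, so actual draws could cluster near a dose or far from one. And limiting extra punctures in incapacitated intensive care patients is a deliberate and reasonable choice. Neither removes the problem: clustering would be uncontrolled, and the timed ghrelin draws and the baseline draw are already planned. A laboratory manual, if one exists, might allow hormones to be run on those draws, but the protocol does not say so.

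**Conclusion.** The concern holds in a limited form. As written, the protocol collects the four fast-responding hormones at times unrelated to the infusion and names no pre-dose value, although it times the ghrelin sample in the same paragraph. Under 12-hour spacing, evenly spread draws and the quoted half-lives, about three quarters to nine tenths of samples (74% to 89%) would follow clearance of the drug to about 3%, or 66% to 92% across reasonable cut-offs.

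Short-lived hormone effects may be missed or diluted. The extent cannot be fixed from the documents, because the response duration is not given. A null hormone result would be hard to interpret, but not void. The point concerns a secondary biomarker and does not touch the primary CPC analysis.

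**What to change.** In sections 7.3 and 7.1.2:
- Measure cortisol, growth hormone, prolactin and ACTH in the timed ghrelin draws already planned on days 1 and 3.
- Measure the same four hormones in the existing day 0 baseline draw, and use that value as a covariate.
- Record every draw time relative to both the start and the end of the infusion. This also settles how the 30±15 minutes is to be read.
- Leave IGF-1 at routine times.
- On day 2, where no timed ghrelin draw exists, keep the routine draw, record its time and treat the result as supportive.

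The documents do not show that 30±15 minutes is the peak for each hormone. The gain is a common, known time shortly after the infusion, when by step 3 an appreciable amount of ghrelin is still present at half-lives of 27 to 31 minutes (less at 10 minutes).

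The cost is a few millilitres more blood, one extra hormone panel per patient at baseline, and the recording of times. No puncture is added beyond those already planned.
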